5.3 Inferential Analysis

No statistical tests are performed due to the small sample size.

DFS and OS will be described by means of Kaplan-Meier method. Estimates of median DFS and OS rates for specific time points (at e.g. 12, 24 and 36 months) will be provided with the associated 95% confidence limits.

6. SAFETY ANALYSIS

Safety analyses will be performed for the Safety population.

6.1 Extent of Exposure

Detailed information on study drug administration will be provided in data listings.

6.2 Adverse Events

The following information will be analyzed descriptively and corresponding details on the subject level will be provided in data listings.

6.2.1 Data Points

- Adverse Event Overview
 - o Any AE
 - Any AE of clinical interest
 - o Any related AE
 - o Any severe AE
 - Any AE grade 2-4
 - Any related severe AE
 - o Any related AE grade 2-4
 - o Any SAE
 - Any related SAE
 - Any AE requiring study treatment dose modification
 - o Any AE requiring study treatment discontinuation
- Adverse Events by maximum severity
 - o Any AE
 - o Any related AE
- Adverse Event by highest relationship
 - o Any AE
 - o Any AE grade 2-4

Adapted from:

STAT03_A Statistical Analysis Plan Version 6.0, Effective Date 16-Feb-2018

Confidential and intellectual property of Assign DMB. No part of this document or its contents may be duplicated, referenced, published or otherwise disclosed in any form or by any means without prior written consent of Assign DMB.

- o Any SAE
- Adverse Events by SOC and preferred term
 - o Any AE
 - Any related AE
 - Any AE grade 2-4
 - o Any related AE grade 2-4
 - Any SAE
 - Any related SAE
 - Any AE requiring study treatment discontinuation
- 6.2.2 Definition
 - Severe AE: AEs with severities of Grade 3-5 (severe or medically significant, severe or life threatening, death) will be considered as severe AEs
 - Missing causality assessment for adverse events will lead to handling of the AE as "related", see Section 7.3 of the CSP.

6.2.3 Inferential Analysis

AE summary tables will provide the number and percentage of patients with AEs and the 95 % confidence intervals for the event rates according to Wilson.

6.3 Laboratory Parameters

The following information will be analyzed descriptively and corresponding details on the subject level will be provided in data listings.

6.3.1 Data Points

- Hematology
 - o basophils absolute
 - o eosinophils absolute
 - o erythrocytes
 - o hemoglobin
 - o leukocytes
- Clinical chemistry and coagulation
 - o ALT
 - o AST
 - o activated partial thromboplastin
 - time
 - albumin absolute
 - o calcium
 - o creatinine

- o lymphocytes absolute
- o monocytes absolute
- o neutrophils absolute
- o platelets
- o creatinine clearance
- o LDH
- o magnesium
- o phosphate
- o potassium
- o prothrombin time relative
- o **sodium**

Adapted from:

STATO3_A Statistical Analysis Plan

Version 6.0, Effective Date 16-Feb-2018

Page 15 of 23

Confidential and intellectual property of Assign DMB. No part of this document or its contents may be duplicated, referenced, published or otherwise disclosed in any form or by any means without prior written consent of Assign DMB.

| TSH | 0 | free T3 |
|-----------------|---|---------|
| total bilirubin | 0 | free T4 |

The following variables will be analyzed descriptively:

• Absolute values by time point

0

0

- Absolute change from screening values by time point •
- Values above and below normal range by time point •

Conversion of laboratory parameters will be performed from a study site specific laboratory unit into the unit to be used in the statistical analysis via the following formula:

Value in analysis unit = value in study site specific unit * conversion factor •

The following units will be used as standard units:

| Parameter | Unit used for Analysis |
|------------------------------------|------------------------|
| Clinical chemistry and coagulation | on |
| ALT | U/I |
| AST | U/I |
| albumin absolute | g/l |
| calcium | mmol/l |
| creatinine | mg/dl |
| creatinine clearance | ml/min |
| LDH | U/I |
| magnesium | mmol/l |
| phosphate | mmol/l |
| potassium | mmol/l |
| prothrombin time relative | % |
| sodium | mmol/l |
| TSH | mU/I |
| total bilirubin | mg/dl |
| free T3 | ng/l |
| free T4 | ng/l |
| Tumor marker | |
| CEA | µg/I |
| Cyfra 21-1 | µg/I |

| Parameter | Unit used for Analysis | | | | |
|------------------------------------|------------------------|--|--|--|--|
| Clinical chemistry and coagulation | | | | | |
| ALT | U/I | | | | |
| AST | U/I | | | | |
| albumin absolute | g/l | | | | |
| calcium | mmol/I | | | | |
| creatinine | mg/dl | | | | |
| creatinine clearance | ml/min | | | | |
| LDH | U/I | | | | |
| magnesium | mmol/I | | | | |
| phosphate | mmol/I | | | | |
| potassium | mmol/I | | | | |
| prothrombin time relative | % | | | | |
| sodium | mmol/I | | | | |
| тѕн | mU/I | | | | |
| total bilirubin | mg/dl | | | | |
| free T3 | ng/I | | | | |
| free T4 | ng/l | | | | |

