In- / Exclusion criteria	Х						
Biomarkers (blood sample)		Х	Х	Х	Х	Х	
Tumor tissue ⁹	Х				Х		
HR-QoL	Х			Х		Х	
Treatment (V1/V2)		Pembrolizumab 200 mg i.v	Pembrolizumab 200 mg i.v				

0316-ASG / NEOMUN

Study Phase Procedure	Screening	Treatment phase		Pre- Surgery	Dis-charge	End of treatment	Follow-up
Visit	SCR	V1	V2	PS	D	EOT	FU1 – FUx
Time windows	Day - 28 to 0	Day 1	Day 21 +/- 3 days	Day 43-50	Day 60-74	6 wks. after surgery	every 3 months
Concomitant medication	Х		Continuously				
Concomitant procedures	Х		Continuously				
Adverse events	Х	Continuously			X ⁷		
Subsequent cancer therapy							Х
Survival status							Х

¹ if clinically indicated. Consult a specialist if clinically abnormal and exclude any immune-related myocarditis.

² Full examination is required at baseline and end of treatment. Focused clinical examination shall prevail throughout the course of treatment.

³ Body height will only be measured at screening.

⁴ Full blood count including blood differential test will be performed at baseline, after start of treatment (V2) and further indicated time points throughout treatment and at end of study.

⁵ Sodium, potassium, calcium, magnesium, phosphate, AST, ALT, PTT/INR, LDH, total bilirubin, creatinine, creatinine clearance, albumin, tumor marker CEA, Cyfra 21-1

⁶ To be done at baseline and 3 weeks after start of treatment (V2) and further indicated time points throughout treatment and at end of study. If rising TSH is detected, a full assessment of fT3 and fT4 shall be performed and signs of hormone depletion shall be monitored clinically.

⁷ Follow-up of ongoing SAEs until resolution or stabilization. Serious adverse events are recorded until 90 days after last dose of IMP or for 6 weeks after surgery if the subject initiated new anticancer therapy (e.g. radiochemotherapy). Pregnancies occurring in a study subject are recorded from time of signed informed consent until 120 days after last dose of IMP.

⁸ Repeat assessment if SCR assessment is older than 7 days.

⁹ Post-op. tumor regression grading.

Safety reporting contact information (SAE / Pregnancy)

In the case of a serious adverse event (SAE) or pregnancy safety desk must be contacted within 24 hours.

Contact details for safety reporting are provided in the Investigator Site File.

The safety desk will inform MSD Germany Pharmacovigilance (Email:

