- 18. Other active malignancy requiring treatment

Exceptions include basal cell carcinoma of the skin or squamous cell carcinoma of the skin that has undergone potentially curative therapy or in situ cervical cancer.

19. Lactating or pregnant women, women of child-bearing potential who do not agree to the usage of highly effective contraception methods (allowed

methods of contraception, meaning methods with a rate of failure of less than 1% per year are implants, injectable contraceptives, combined oral contraceptives, intrauterine pessars (only hormonal devices), sexual abstinence or vasectomy of the partner). Women of childbearing potential must have a negative pregnancy test (serum β -hCG) at Screening.

- 20. Any psychiatric illness that would affect the patient's ability to understand the demands of the clinical trial
- 21. Patient has already been recruited in this trial
- 22. Patient who has been incarcerated or involuntarily institutionalized by court order or by the authorities § 40 Abs. 1 S. 3 Nr. 4 AMG.
- 23. Patients who are unable to consent because they do not understand the nature, significance and implications of the clinical trial and therefore cannot form a rational intention in the light of the facts [§ 40 Abs. 1 S. 3 Nr. 3a AMG].

5 Schedule of Assessment and Procedures

Please refer to the Schedule of Assessments for an overview.

Data will be collected via an electronic Case Report Form (eCRF) for each eligible patient. The investigator should confirm eligibility of the patient according to the inclusion and exclusion criteria of the study. All patients will provide written Informed Consent before any study specific assessment is performed. A study specific assessment is defined as a procedure that is not part of the routine assessments performed for diagnostic purposes or standard care. Screening assessments should occur within 28 days of the first administration of study drug.

Patients not meeting the inclusion/exclusion criteria will not be enrolled into the study. Patients should receive their first dose of study treatment as soon as possible after they have been intended to be treated with study medication.

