5.2.2 Treatment Phase

For V1 no particular assessments are required. However, the following assessments need to be repeated if the Screening assessment is older than 7 days measured from first dose of IMP: Hematology, pregnancy test, clinical chemistry, coagulation, vital signs. ConMed and AE documentation may need to be updated if required.

During treatment phase the following assessments and procedures will be performed for V2 unless a different time point is mentioned specifically:

Cardiac evaluation	12-lead ECG, transthoracic echocardiogram (TTE)
	if clinically indicated
Physical examinations and	Physical examination
vital signs	Body weight, BSA
	Vital signs measurements will include body
	temperature, pulse and blood pressure
ECOG performance status	Day 1 of each immunotherapy cycle, see

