8.4 Methods of Statistical Analysis

8.4.1 General statistical considerations

The statistical evaluation will be carried out by sponsor delegate . Statistical analysis is based on the International Conference on Harmonization (ICH) Guidelines "Structure and Content of Clinical Study Reports" and "Statistical Principles for Clinical Trials".

All data recorded in the eCRF describing the sample, the efficacy and the safety will first be analyzed descriptively. Categorical data will be presented in tables with frequencies and percentages.

Continuous data will be summarized with at least the following: frequency (n), median, quartiles, mean, standard deviation (standard error), minimum and maximum. Descriptive analyses will be summarized.

Statistical test between changes of parameters over time will be performed for continuous as well as categorical variables. One way repeated measures analysis of

variance, Wilcoxon signed rank test, Fisher's exact test and other appropriate tests will be used where applicable. Further details will be given in the Statistical Analysis Plan.

Number of patients with protocol deviations during the study and listings describing the deviations will be provided.

For the analysis of Adverse Events, summary tables will be generated for the incidence of AEs overall and by severity. This will also be done for Serious Adverse Events. The AE summary tables will provide the number and percentage of patients with adverse events. All safety analyses will be performed within the safety population.

For laboratory parameters, the distribution over time (mean values) as well as changes from randomization will be computed and reported with descriptive statistics.

The details of the statistical analysis will be defined in a Statistical Analysis Plan, which will be prepared before database closure.

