2.4 Blinding and Randomization

As it is an open-label and single arm study, principles of blinding and randomization are not applicable.

2.5 **Descriptive Analyses**

- Descriptive analyses of continuous variables (summary statistics) will be described with the number of nonmissing observations, arithmetic mean, standard deviation (±SD), median, quartiles (Q1 and Q3) and range (minimum and maximum).
- Categorical variables (frequency statistics) will be described with the number of non-missing observations and percentages (%).

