7.1.4 Safety Analysis

| No | Legend | Content | | | |
|----------------|--|---|--|--|--|
| Adverse Events | | | | | |
| 14.4.1 | Adverse Events Overview (Safety Population) | Any AE Any AE of clinical interest Any related AE Any severe AE Any AE grade 2-4 Any related severe AE Any related AE grade 2-4 Any related AE grade 2-4 Any SAE Any related SAE Any AE requiring treatment discontinuation Any AE requiring treatment dose modification | | | |
| 14.4.2 | Adverse Events by Maximum Severity (Safety Population) | Any AE Any related AE | | | |
| 14.4.3 | Adverse Event by Highest Relationship (Safety Population) | Any AE Any AE grade 2-4 Any SAE | | | |
| 14.4.4 | Adverse Events by SOC and Preferred Term (Safety Population) | Any AE Any AE grade 2-4 Any related AE Any related AE grade 2-4 Any SAE Any related SAE Any AE requiring study treatment discontinuation | | | |
| Laborato | bry Parameters | | | | |
| 14.4.5 | Hematology Values over Time (Safety Population) | - | | | |
| 14.4.6 | Hematology Value's Change from Baseline (Safety Population) | | | | |
| 14.4.7 | Hematology Values above and below Normal Range by Time Point (Safety Population) | | | | |
| 14.4.8 | Clinical Chemistry and Coagulation Values over Time (Safety Population) | | | | |
| 14.4.9 | Clinical Chemistry and Coagulation Value's Change from Baseline (Safety Population) | | | | |

Adapted from: STAT03_A Statistical Analysis Plan

Version 6.0, Effective Date 16-Feb-2018

Confidential and intellectual property of Assign DMB. No part of this document or its contents may be duplicated, referenced, published or otherwise disclosed in any form or by any means without prior written consent of Assign DMB.

| 14.4.10 | Clinical Chemistry and Coagulation Values above and below Normal Range by Time Point (Safety Population) | | |
|----------|--|---|------------------|
| Other Sa | fety Parameters | | |
| 14.4.11 | ECOG Status (Safety Population) | | |
| 14.4.12 | Vital Signs (Safety Population) | ٠ | Blood pressure |
| | | • | Heart rate |
| | | • | Body temperature |
| | | • | Body weight |

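### Laboratory change is computed from screening even when a later pre-dose repeat exists, and the reference point is named three different ways

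*SAP*

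**What the plan says.** **Reference value.** Among the laboratory summaries in SAP 6.3.1 is "Absolute change from screening values by time point". The tables that report it carry another label: 14.4.6 is "Hematology Value's Change from Baseline (Safety Population)" and 14.4.9 is "Clinical Chemistry and Coagulation Value's Change from Baseline (Safety Population)". The SAP does not define baseline for laboratory data. Protocol 8.4.1 uses a third term: "changes from randomization will be computed and reported with descriptive statistics". SAP 2.4 states: "As it is an open-label and single arm study, principles of blinding and randomization are not applicable". SAP 2.14 lists two departures from the protocol, on screening failures in the listings and on tests between time points. The laboratory reference is not one of them.

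**Age of the screening value.** The opening of Protocol section 5 says: "Screening assessments should occur within 28 days of the first administration of study drug".

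**Repeat before dosing.** Protocol 5.2.2 requires nothing at V1 by default. It then names tests, including hematology, clinical chemistry and coagulation, that "need to be repeated if the Screening assessment is older than 7 days measured from first dose of IMP". Footnote 8 to the schedule of assessments, also printed in SAP 1.5, says the same: "Repeat assessment if SCR assessment is older than 7 days". In the schedule TSH has its own row, with no mark at V1.

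**The concern.** The protocol treats a laboratory result more than 7 days old as needing a repeat before treatment starts. The SAP nevertheless keeps the older result as the reference for change, even for patients who have the newer one. Whatever happened to the value between screening and V1 is then counted in the change reported at V2 and at later visits.

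Safety is part of the primary objective, there is no control arm, and SAP 2.14 drops the tests between time points. A reader of Tables 14.4.6 and 14.4.9 has only the descriptive change and will take it as change on pembrolizumab. With three names for the reference point, two programmers could also produce different tables from the same plan. One would follow the word screening in 6.3.1. The other would read baseline in the table titles as the last value before dosing.

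**Working it through.** No sample size, power or error rate in the plan depends on this choice, so there is no stated figure to reproduce. The check has three parts.

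**1. How much of the interval lies before the first dose**

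Inputs: *s* = days from the reference value to the first dose, up to 28 (Protocol section 5); *v* = study day of V2, 21 ± 3 (schedule of assessments); first dose on day 1.

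Share of the reference-to-V2 interval before any drug = *s* / (*s* + *v* − 1).

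| Reference value | V2 day 18 | V2 day 21 | V2 day 24 |
|---|---|---|---|
| Screening on day -28 | 28/45 = 62% | 28/48 = 58% | 28/51 = 55% |
| Last pre-dose value, worst case under the 7-day rule (*s* = 7) | 7/24 = 29% | 7/27 = 26% | 7/30 = 23% |
| V1 repeat on the day of dosing (*s* = 0) | 0% | 0% | 0% |

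If screening is at most 7 days old, no repeat is due and the two definitions pick the same value. They differ only for patients with a V1 repeat. Protocol 5.3 removes a patient only after a delay of more than 31 days. At *s* = 31 the middle column would be 31/51 = 61%. The 28-day and 31-day limits need to be reconciled with each other.

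**2. What this could do to a mean change**

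The documents give no standard deviation, within-patient correlation, pre-dose drift, or share of patients with a repeat. The following is illustration under assumptions only.

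- Drift carried into the mean change = share with a repeat × drift in SD. With an assumed share of 25% to 100% and an assumed drift of 0.1 to 0.3 SD, this runs from 0.25 × 0.1 = 0.025 SD to 1 × 0.3 = 0.30 SD.
- For scale, the 95% half-width of a mean change with n = 30 is 1.96 × √(2(1 − ρ)/30). With an assumed correlation ρ of 0.9 to 0.5 it is 0.16 to 0.36 SD.

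The carried drift therefore ranges from negligible to about the size of the sampling error, depending on inputs that the documents do not supply.

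**3. Whether selection on eligibility values adds to it**

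If a screening value must lie on the acceptable side of a limit *k* SD from the mean, the expected shift of the group mean at a later measurement is (1 − ρ) × φ(*k*)/Φ(*k*). With assumed ρ of 0.9 to 0.5:

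- *k* = 1: 0.03 to 0.14 SD
- *k* = 2: 0.006 to 0.03 SD
- *k* = 3: at most 0.002 SD

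Unless a limit cuts into the bulk of the distribution, this is too small to matter with 30 patients.

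**The case against.** The strongest defence is that little depends on these two tables. The primary safety endpoint is the frequency and severity of adverse events. Laboratory change is descriptive, with no test or stopping rule attached. SAP 6.3.1 also plans absolute values and values outside the normal range by time point (Tables 14.4.5, 14.4.7, 14.4.8 and 14.4.10), and Listings 16.2.4.14 and 16.2.4.15 show every value by visit. If V1 is displayed as a time point, its own change from screening shows the drift openly. All of this stands, and it limits the weight of the point. It does not rescue the definition: the SAP does not say that V1 repeats are displayed, and no other part of it moves the reference away from screening.

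Four stronger readings are tempting, and the documents do not support them.

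- *The tests are always repeated before dose 1.* The repeat is conditional on the age of the screening result, and the share of patients concerned is unknown.
- *Regression to the mean produces a sizeable bias because screening values had to pass entry limits.* The familiar (1 − r) × deviation describes one patient far from the mean. Patients on the other side move the opposite way, so it is not a shift of the group mean. The group effect of one-sided limits is small (part 3 of the working) and arises only for parameters with an entry limit. Coagulation eligibility in Protocol 4.2 is already tied to the last 7 days before therapy, so a V1 coagulation value may itself be the selected one.
- *Change is the only laboratory reference in the trial.* The absolute-value and out-of-range tables show otherwise.
- *Vital signs share the defect because they too are repeated at V1.* SAP 6.4.1 and Table 14.4.12 specify no change from baseline for vital signs.

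**Conclusion.** The point holds as a definitional defect in descriptive safety output. For patients with a V1 repeat, SAP 6.3.1 selects a reference up to 28 days old when a later pre-dose value has been collected. In the extreme case, more than half of the reported interval (58% with V2 on day 21) precedes any drug, against at most 26% with the last pre-dose value. That comparison assumes that the 7-day rule is followed and that V1 samples are drawn before the infusion.

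The documents show that drift can enter the reported change. They do not show that it does, or by how much. The inconsistency between randomization, screening and baseline needs no assumption: it is on the page, and SAP 2.14 does not record it.

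The reach is limited. Patients screened within 7 days of dosing are unaffected. TSH gains nothing as long as the schedule is followed and no V1 sample is taken. No adverse-event grade, test, sample size or primary endpoint changes. The change is still worth making because it improves the tables with data already collected.

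**What to change.** 1. In SAP 6.3.1, define laboratory baseline as the last non-missing value before the first dose of pembrolizumab: the V1 repeat where done, otherwise screening. Listing 16.2.4.14 holds a sample date but no time, so state the convention for a V1 sample dated on the day of the first dose.
2. Use this definition in Tables 14.4.6 and 14.4.9 and Listings 16.2.4.14 and 16.2.4.15, and use the word baseline in 6.3.1 as well.
3. Compute change from V2 onward. Show V1 values as a separate time point labelled pre-dose, without a change column.
4. Record in SAP 2.14 that this replaces the reference to randomization in Protocol 8.4.1.

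The cost is a few sentences in the SAP and one derived baseline flag. No new data, visits or tests are needed.

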 For the time period beginning at start of treatment through 6 weeks following surgery, any ECI, or follow up to an ECI, whether or not related to IMPs, must be reported within 24 hours of investigators awareness to safety desk.

Other reportable events: For each patient any 'other reportable' event occurring until 6 weeks after surgery must be reported immediately (within 24 hours) after investigator's awareness to the safety desk.

Pregnancy: Pregnancies occurring during study treatment and up to 120 days after last dose must be reported by the investigator on the **Pregnancy Report Form** within 24 hours after awareness to the safety desk.

Follow up case reports have to be provided as new information becomes available. If an SAE is experienced in addition to or related to the pregnancy e.g. an induced or spontaneous abortion, also an SAE Report has to be sent to the safety desk within 24 hours / GCP-V § 12(4) after first knowledge.

Overdose: If an adverse event(s) is associated with ("results from") the overdose of IMP, the adverse event(s) is reported as a **serious adverse event**, even if no other seriousness criteria are met. An SAE Report has to be sent to the safety desk within 24 hours of investigators awareness.

If an overdose is administered without any associated clinical symptoms or abnormal laboratory results, the overdose is reported as a **non-serious Event of Clinical Interest** (ECI), using the terminology "accidental or intentional overdose without adverse effect." An SAE Report has to be sent to the safety desk within 24 hours of investigators awareness.

Abnormal Laboratory results: Abnormal laboratory test results will be recorded on the laboratory results pages of the eCRF. Laboratory-test-value abnormalities should additionally be considered an AE in case they are:

- 1. Accompanied by clinical symptoms
- 2. Leading to a change in study medication (e.g. dose modification, interruption or permanent discontinuation)
- 3. Requiring a change in concomitant therapy (e.g. addition of, interruption of, discontinuation of, or any other change in a concomitant medication, therapy or treatment)

In general it is the investigator's responsibility to review all abnormal laboratory results and to determine if a given value represents a clinically significant change compared to previously obtained values and results in an Adverse Event or not.

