8.4.4 Safety evaluation

Adverse events:

All information recorded such as onset date, stop date, duration, maximum intensity, seriousness, relationship to study drug and outcome will be listed.

Summary tables will be presented. These tables provide the number and percentage of patients with adverse events. Associated adverse event tables present the total number of patients reporting at least one specific event and the maximum toxicity grade. Thus, patients reporting more than one episode of the same event are counted only once by the worst grade per patient.

Tabulations consist of the number and percentages of patients involved per CTC category and CTC term, the highest relation to study drug, and the maximum severity. Special tables will be displayed for CTC grade III / IV adverse events and for adverse events resulting in discontinuation of the trial. Additionally, analysis will be restricted to adverse events judged to be at least possibly related to study drug.

Laboratory parameters:

Abnormal laboratory parameters will be tabulated according to incidence and severity according to NCI CTCAE V4.03 and analyzed descriptively.

9 Independent Data Monitoring Committee

An Independent Data Monitoring Committee (IDMC) has been convened to assess the safety data, and provide recommendations to the Sponsor and Coordinating Investigator upon the stop or continuation of the study. The members of the IDMC serve in their individual capacity and provide their expertise and recommendations. The IDMC will review cumulative study data to evaluate subject safety, conduct an interim analysis and reassess the risk/benefit of the study.

The role and responsibilities of the IDMC are described in detail in a separate IDMC Charter.

10 Data Quality Assurance

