2.14 Changes in the Conduct of the Study or Planned Analysis

The following changes as compared to descriptions in the CSP are described in this SAP:

- According to a sentence in the CSP, all patients' data is included in data listings. During SAP review it was decided to not include screening failure data in all data listings.
- The CSP planned to include statistical tests between time points. During SAP review it was decided to omit such tests due to small sample size.

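### The SAP drops the protocol's CTCAE-graded laboratory tables without declaring it, so laboratory abnormalities not recorded as adverse events get no severity grade

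*SAP*

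**What the plan says.** Protocol 8.4.4 treats adverse events and laboratory parameters under separate subheadings. Under the second it states: "Abnormal laboratory parameters will be tabulated according to incidence and severity according to NCI CTCAE V4.03 and analyzed descriptively". Protocol 8.4.1 makes a further promise of descriptive statistics, which begins "For laboratory parameters, the distribution over time (mean values) as well as changes from".

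SAP 6.3.1 names three laboratory analyses:

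- "Absolute values by time point"
- "Absolute change from screening values by time point"
- "Values above and below normal range by time point"

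SAP 7.1.4 turns these into Tables 14.4.5 to 14.4.10, three for hematology and three for chemistry and coagulation. The two tables of abnormal values are 14.4.7 and 14.4.10, and both are by normal range and time point.

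SAP 2.14 opens its list of departures with "The following changes as compared to descriptions in the CSP are described in this SAP". It has two entries: screening-failure data in listings, and the omission of statistical tests between time points. Laboratory grading is not mentioned.

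Protocol 7.5.2 governs when a laboratory abnormality should also be treated as an AE. It gives three triggers: clinical symptoms, a change in concomitant therapy, and the following: "Leading to a change in study medication (e.g. dose modification, interruption or permanent discontinuation". It then leaves the investigator to review all abnormal results and decide whether a value is a clinically significant change amounting to an AE.

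**The concern.** The protocol promises a graded laboratory table in addition to the AE tables. The SAP puts an ungraded one in its place and does not say so. A reader of SAP 2.14 would conclude that the laboratory analysis follows the protocol.

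What is at stake is the systematic grading of measured values. In an open-label, single-arm, single-centre trial, a graded table built from the values themselves does not depend on whether the investigator recorded an AE. Without it, the severity of a laboratory abnormality reaches the tables as a grade only if the abnormality was first recorded as an AE.

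**Working it through.** The point rests on comparing the texts. The plan gives no figure to reproduce.

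**Step 1. Commitment against delivery.**

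| Item | Protocol | SAP |
|---|---|---|
| Values and changes over time | Promised, 8.4.1 | Delivered: Tables 14.4.5, 14.4.6, 14.4.8, 14.4.9 |
| Abnormal values by incidence and CTCAE grade | Promised, 8.4.4 | Not planned; Tables 14.4.7 and 14.4.10 use normal range by visit |
| Grade in laboratory listings | Not specified | None; Listings 16.2.4.14-15 show value, limits, out-of-range flag, clinical relevance and causal relationship |
| Declaration of the change | n/a | Not in 2.14 |

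**Step 2. Which abnormalities still get a grade.** Protocol 7.5.2 requires a CTCAE grade for every AE. SAP 6.2.1 tabulates AEs by maximum severity and, for grade 2-4, by system organ class and preferred term. Listing 16.2.4.2 has a grade column. A laboratory abnormality recorded as an AE is therefore graded. One that meets none of the three triggers and is not judged an AE is not.

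**Step 3. Where such abnormalities are most plausible.** The schedule sets four laboratory visits after the first dose: V2, pre-surgery, discharge and end of treatment. Treatment is two doses, at V1 and V2. So 4 - 1 = 3 of these visits normally follow the last planned dose. At those three there is usually no study medication left to modify, interrupt or stop, and that trigger has little or no scope.

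**Step 4. What normal-range counts cannot show.** Protocol 4.2 admits AST and ALT below 2.5 x ULN, bilirubin below 1.5 x ULN, and creatinine above 1.5 x ULN if clearance is at least 60 mL/min. As an illustration, take one patient who enters with ALT at 2 x ULN and stays there, and another who enters in range and rises to 10 x ULN. After the rise, Table 14.4.10 counts both as above range.

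**Step 5. Per-visit counts against per-patient incidence.** As an illustration, assume 30 treated patients and the three visits after the last planned dose.

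- One patient above range at all three visits: 1/30 = 3.3% at each visit. Patients ever affected: 1/30 = 3.3%.
- Three different patients, each above range at one visit: 1/30 = 3.3% at each visit. Patients ever affected: 3/30 = 10.0%.

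The per-visit table is the same in both cases. It does not give per-patient incidence or worst grade. Protocol 8.4.4 does count AEs once per patient by worst grade.

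**The case against.** The strongest case on the other side is that little is lost.

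- **The AE route is wider than the three triggers.** A reader might infer that under Protocol 7.5.2 a laboratory value becomes an AE only if a trigger is met. The text does not say so. It adds investigator review of all abnormal results, and Protocol 7.2.1 includes abnormal laboratory findings in the AE definition. An asymptomatic rise after the last dose can still be recorded and graded. This stands, but it makes grading depend on judgment.
- **Treatment may itself trigger an AE.** Protocol 6.3.2 lists corticosteroids for hepatic events of grade 2 and of grade 3-4. Where these are given, the concomitant-therapy trigger is met. This stands for events judged related to pembrolizumab, to which that guidance is limited.
- **Events of clinical interest have their own reporting line.** Protocol 7.2.3 covers AST or ALT at least 3 x ULN combined with bilirubin at least 2 x ULN and alkaline phosphatase below 2 x ULN. These are reportable through 6 weeks after surgery whether or not related. An isolated transaminase rise does not qualify.
- **Extreme values remain visible.** SAP 2.5 requires minimum and maximum, and the listings show every value with its limits. This stands, so the failure to distinguish a small from a large elevation applies to Tables 14.4.7 and 14.4.10 only. A maximum at a visit still does not say how many patients reached a given grade.
- **The primary endpoint concerns AEs.** The primary safety endpoint is the frequency and severity of AEs, not graded laboratory values. This stands.

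None of these points explains the absence from SAP 2.14 or supplies the table promised in Protocol 8.4.4.

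**Conclusion.** The mismatch is certain on the text: Protocol 8.4.4 promises CTCAE-graded laboratory tables, the SAP plans none, and SAP 2.14 does not declare the change. The consequence is limited to abnormalities that are untreated, asymptomatic and not judged an AE by the investigator. Those are reported without a severity grade. The normal-range tables also mix patients out of range at entry with those who worsen, and give no worst grade per patient.

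Two stronger readings are tempting, and the documents do not support them. One is that the severity of laboratory toxicity goes unreported altogether. It does not: abnormalities recorded as AEs keep their CTCAE grade. The other is that the primary safety endpoint is left unanalysed. That endpoint is defined on AEs, which the SAP does tabulate by grade.

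The number of patients affected cannot be derived from the documents. Each one is 1/30 = 3.3 percentage points, if all 30 are treated. The view that the gap falls mainly on the three later visits assumes that the second dose was given or treatment had already stopped. If that dose is delayed, the study-medication trigger stays available for longer. This should be corrected before the analysis; it does not undermine the trial.

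**What to change.** Add to SAP 6.3.1 and 7.1.4 a table of the worst post-dose CTCAE v4.03 grade per patient, for each parameter that can be graded from the collected values and limits. Give number and percent by grade in the Safety population and show baseline grade, for example as a shift table. Protocol 8.4.4 asks for incidence and severity, so the shift layout is a recommendation; it is what separates patients abnormal at entry from those who worsen. Tables 14.4.7 and 14.4.10 can stay.

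Add a grade column to Listings 16.2.4.14-15.

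State three rules with the table:

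- which value is baseline, since SAP 6.3.1 measures change from screening but the schedule calls for a repeat at V1 when the screening result is older than 7 days;
- whether unscheduled repeats, which Protocol 7.6.5 calls for, count towards the worst grade;
- that high and low abnormalities are graded separately where both are graded.

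If the sponsor prefers not to grade, the omission should at least be declared and justified in SAP 2.14. That would cure the silence but leave the gap.

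The cost is programming only. Values and units are already in Listings 16.2.4.14-15, and normal limits by sex, age and date are in Listing 16.2.4.13. No new data collection is needed.
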